**Randomized, Double-Masked, Pilot Study Comparing the Safety and Efficacy
of Two Dosing Regimens of TP-03 for the Treatment of Meibomian Gland
Dysfunction in Patients with *Demodex* Lid Infestation (Ersa)**

Protocol Number: TRS-008

[REDACTED]

[REDACTED]

[REDACTED]

[REDACTED]

IND Sponsor: Tarsus Pharmaceuticals, Inc.

NCT05454956

PROTOCOL SUMMARY

TITLE	Randomized, Double-Masked, Pilot Study Comparing the Safety and Efficacy of Two Dosing Regimens of TP-03 for the Treatment of Meibomian Gland Dysfunction in Patients with Demodex Lid Infestation (Ersa)
TEST ARTICLE	TP-03, lotilaner ophthalmic solution, 0.25%
OTHER TEST ARTICLE	Vehicle of TP-03 to maintain masking of BID dosing
OBJECTIVE	
To evaluate the safety and efficacy of TP-03, 0.25%, BID versus TID dosing for the treatment of meibomian gland dysfunction in patients with Demodex lid infestation.
 
Efficacy will be evaluated by the assessment of lower lid meibomian gland secretion, erythema of the lid margins, [REDACTED], [REDACTED].
 
Safety will be determined by assessing adverse effects related to treatment [REDACTED]
 
[REDACTED]

CLINICAL HYPOTHESIS	Treatment with TP-03, 0.25%, TID will result in a greater improvement from baseline than BID treatment for 85 days in the signs [REDACTED] of MGD with no significant increase in ocular irritation.
STUDY DESIGN	Prospective, randomized, two-arm, double-masked, parallel treatment study
NUMBER OF PARTICIPANTS	Up to 40
PARTICIPANT POPULATION	Participants with evidence of meibomian gland dysfunction in the presence of Demodex infestation
DESCRIPTION OF SITES	Up to six sites in the United States
STUDY DURATION	Approximately 9 months
RANDOMIZATION	1:1
STUDY VISITS	Study visits will take place at Day 1, Day 15, Day 29, Day 43, Day 57, Day 85 and Day 115
SAFETY MEASURES	
 • Adverse events • [REDACTED] • Slit lamp biomicroscopy findings
EFFICACY MEASURES	
 • Lower lid meibomian gland secretion assessment 
 ○ Total meibomian gland score

Clinical Research Protocol

Protocol TRS-008

[figure not shown]
01-Feb-2023

	
• Lid margin erythema
STATISTICAL CONSIDERATIONS	This is a pilot study to compare the safety and efficacy of two different dosing regimens, BID and TID, of TP-03 for the treatment of MGD. There are no prior data available to perform a sample size estimate. The sample size of 40 participants was selected based on clinical and practical considerations.
STATISTICAL ANALYSIS PLAN	
Safety measures will be summarized for each treatment regimen and both treatment regimens combined using descriptive statistics.
 
Efficacy measures will be compared between dosing regimens as the change from baseline using either the t-test or Wilcoxon rank-sum test as appropriate. Comparisons will be two-sided using an α of 0.05. No adjustment will be made for multiple comparisons.

TABLE OF CONTENTS

1.	ABBREVIATION TABLE.....	7
2.	INTRODUCTION AND RATIONALE.....	8
2.1.	MEIBOMIAN GLANDS	8
2.2.	MEIBOMIAN GLAND DYSFUNCTION	8
2.6.	POTENTIAL RISKS AND BENEFITS	13
3.	TREATMENTS.....	14
3.1.	TP-03 AND VEHICLE	14
4.	STUDY OBJECTIVE.....	15
5.	STUDY DESIGN.....	15
6.	STUDY POPULATION	15
7.	STUDY OUTCOME MEASUREMENTS.....	18
7.1.	EFFICACY PARAMETERS.....	18
7.2.	SAFETY PARAMETERS	18
8.	CLINICAL EVALUATIONS	18
8.1.	DAY 1	18
8.2.	DAYS 15 (± 4 DAYS) AND 29 (± 5 DAYS)	19
8.3.	DAY 43 (-7/+6 DAYS) AND DAY 57 (-7/+10 DAYS).....	20
8.4.	DAY 85 (-13/+7 DAYS).....	20
8.5.	DAY 115 (+60 DAYS)	21
9.	STUDY DRUG	21
10.	STUDY PROCEDURES AND ASSESSMENTS	22
10.1.	INFORMED CONSENT	22
10.2.	PARTICIPANT ID ASSIGNMENT.....	22
10.3.	STUDY TREATMENT COMPLIANCE	23
10.4.	VISIT SCHEDULE AND EXAMS	23
10.5.	STUDY EXIT	23
11.	EARLY TERMINATION AND PARTICIPANT DISCONTINUATION.....	23

12. STATISTICAL CONSIDERATIONS AND ANALYSIS	25
12.1. SAMPLE SIZE	25
12.2. RANDOMIZATION.....	25
12.3. GENERAL CONSIDERATIONS	25
12.4. MISSING DATA	25
12.5. STUDY OUTCOMES	25
12.6. STATISTICAL HYPOTHESES.....	26
12.7. STATISTICAL ANALYSES	26
12.8. INTERIM ANALYSIS	27
12.9. FINAL REPORT	27
13. ETHICAL AND REGULATORY CONSIDERATIONS	27
14. INVESTIGATOR RESPONSIBILITIES.....	28
15. CONCOMITANT MEDICATIONS AND THERAPIES	29
15.1. PROHIBITED CONCOMITANT MEDICATIONS/PROCEDURES	29
16. ADVERSE EVENTS AND SERIOUS ADVERSE EVENTS	30
16.1. DEFINITION OF ADVERSE EVENTS (AE)	30
16.2. DEFINITION OF SERIOUS ADVERSE EVENTS (SAE)	30
16.3. CLASSIFICATION OF AN ADVERSE EVENT	30
16.4. TIME PERIOD AND FREQUENCY FOR EVENT ASSESSMENT AND FOLLOW-UP	32
16.5. ADVERSE EVENT REPORTING.....	33
16.6. SERIOUS ADVERSE EVENT REPORTING.....	33
16.7. REPORTING EVENTS TO PARTICIPANTS	34

1. ABBREVIATION TABLE

ADE	Adverse drug effect
AE	Adverse event
APEC	Asociación para Evitar la Ceguera
BID	Twice a day
CA	California
CDVA	Corrected distance visual acuity
CRF	Case report form
eCRF	Electronic case report form
EMEA	European Medicines Evaluation Agency
ETDRS	Early Treatment Diabetic Retinopathy Study
EU	European Union
FDA	Food and Drug Administration
GABA _A Rs	GABA-gated chloride channels
GCP	Good clinical practice
GLP	Good laboratory practice
ICH	International Conference on Harmonisation
ID	Identification
IND	Investigational New Drug
IOP	Intraocular pressure
IPL	Intense pulsed light
IRB	Institutional Review Board
IUPAC	International Union of Pure and Applied Chemistry
LOCS	Lens opacities classification system
MedDRA	Medical Dictionary for Regulatory Activities
MD	Doctor of medicine
MGD	Meibomian gland dysfunction
NADA	New Animal Drug Application
NaFl	Sodium fluorescein
NC	North Carolina
NEI	National Eye Institute
NIBUT	Non-invasive breakup time
NOAEL	No observed adverse effect level
NOEL	No observed effect level
OD	Doctor of optometry
SAE	Serious adverse event
SPEED	Standard Patient Evaluation of Eye Dryness questionnaire
SUSAR	Serious and unexpected suspected adverse reaction

[REDACTED]	[REDACTED]
TID	Three times a day
TP-03, 0.25%	Lotilaner ophthalmic solution, 0.25%
TRS	Tarsus
US	United States
VA	Visual acuity
VAS	Visual analog scale
WOCBP	Women of childbearing potential

2. INTRODUCTION AND RATIONALE

2.1. MEIBOMIAN GLANDS

Meibomian glands are sebaceous glands within the eyelids that secrete meibum, a compound primarily made of lipids that form the superficial layer of the tear film. Meibum coats the aqueous layer and provides tear film stability and protection against microbial agents.¹ In healthy individuals, there are approximately 25 to 40 glands in the upper eyelid and approximately 20 to 30 in the lower eyelid.² Proper functioning of the glands serves many purposes including minimizing tear film evaporation, enhancing tear film stability, providing a smooth optical surface for the cornea, and sealing the opposing lid margins during sleep.³

2.2. MEIBOMIAN GLAND DYSFUNCTION

Meibomian gland dysfunction (MGD) is a common eyelid disorder⁴ that may well be the leading cause of dry eye disease throughout the world.^{5,6} Published literature cites a global incidence ranging widely from 3.5% to almost 70%.⁷ The incidence of MGD has been found to increase with age⁸⁻¹² and is markedly higher in Asian populations.¹³⁻¹⁵ According to the International Workshop of Meibomian Gland Dysfunction, MGD is a chronic, diffuse abnormality of the meibomian glands, commonly characterized by terminal duct obstruction and/or qualitative/quantitative changes in the glandular secretion. This may result in alteration of the tear film, symptoms of eye irritation, clinically apparent inflammation and ocular surface disease.¹⁶ Characteristic signs of MGD include the release of cloudy meibum or more viscous material on gland expression or an absence of expressible secretion.⁴ Meibomian gland dysfunction should be regarded as a progressive but treatable disease in which therapy may prevent irreversible changes.⁴

Demodex mites have been implicated in several ocular surface diseases including dry eye syndrome¹⁷ associated with MGD.¹⁸⁻²⁰ Luo and colleagues demonstrated that the *Demodex*-positive rate in MGD patients is higher than that in the control group and that *Demodex*-positive patients experienced more severe meibomian gland loss.²¹ Other studies found that *Demodex*-positive patients had more corneal and conjunctival pathologic features.^{22,23} In a retrospective review of clinical results, Gao et al²⁴ identified MGD in addition to ocular demodicosis in seven of 11 subjects. These subjects manifested abnormal lipid film with slow lipid film spread, intermittent trichiasis (n = 5) and subjective lash loss (n = 4) suggestive of damage to the meibomian glands and lash follicles. The authors concluded that *Demodex* potentially causes

MGD, ocular surface inflammation and lash abnormalities. A study by López-Ponce et al²⁵ found that the prevalence of infestation by *D. folliculorum* is high in patients with posterior blepharitis. In addition, they found that parasite density was positively correlated with age and with the occurrence of collarettes on the eyelid border.

Previous studies have found that *Demodex* mites can cause microstructural changes in meibomian glands, which can result in or aggravate MGD.²⁶ A recent comparative study sought to understand the impact of *Demodex* infection on the lipid component of meibum in patients.²⁷ The authors found a significant increase in the levels of (O-acyl)-*w*-hydroxy fatty acids (OAHFAs) in the *Demodex*-positive group suggesting that OAHFAs may be associated with the progression of ocular *Demodex* infections. The authors concluded that *Demodex* exert a significant effect on meibum composition in the human meibomian gland and proposed several possible mechanisms contributing to this change, all involving the movement of bacteria carried or secreted by *Demodex* mites.

Other studies investigated the relationship between the area of meibomian gland loss and parameters of subjective symptoms and tear film. Pult et al²⁸ reported that meibomian gland loss was significantly correlated with lipid layer thickness, tear breakup time and subjective symptoms. Ban et al²⁹ reported that parameters of meibomian gland morphology such as the mean length of meibomian gland ducts and the percentage area of meibomian glands are significantly correlated with tear film parameters including tear breakup time and fluorescein staining. These findings suggest that morphometric analysis using meibography may prove useful for assessing ocular surface conditions.

Currently, there are no FDA-approved pharmaceutical treatments for MGD or *Demodex* blepharitis. For MGD, the LipiFlow thermal pulsation system (Johnson & Johnson Vision), the iLux system (Tear Film Innovations) and the TearCare System (Sight Sciences) are the only devices to receive FDA clearance to date. Other recommendations for the management and treatment of MGD include lid heating, massage, and lid hygiene; topical antibiotics and/or topical steroids; systemic anti-inflammatory antibiotics such as tetracycline; lubricants; meibomian gland probing; and meibomian gland expression. For *Demodex* blepharitis, commercial products are prescribed without substantial evidence of effectiveness.³⁰ In previous clinical trials, systemic ivermectin, metronidazole, their combination and topical tea tree oil have been used to treat blepharitis due to *Demodex* infestation with varying degrees of success.³¹⁻³⁴ It should be noted, however, that terpinen-4-ol, a tea tree oil component, has been shown to be toxic to human meibomian gland epithelial cells in vitro, even at levels 10-fold to 100-fold lower than demodicidal concentrations.³⁵ This study is being performed to compare two dosing regimens of a topical ophthalmic preparation of an established acaricide, TP-03, 0.25%, for the treatment of MGD in the presence of *Demodex* infestation.

Clinical Research Protocol

Protocol TRS-008

[figure not shown]
01-Feb-2023

3. TREATMENTS

[figure not shown]
3.1. TP-03 AND VEHICLE

Lotilaner is the investigational drug substance. Lotilaner is an isoxazoline and inhibits the γ -aminobutyric acid (GABA)-gated chloride channels (GABACls) of arthropods. The GABA-mediated chloride influx leads to hyperpolarization of the cellular membrane and generates an inhibitory postsynaptic potential, which decreases the probability of an action potential.³⁶ Ectoparasites exposed to isoxazolines will exhibit spastic paralysis leading to their starvation and death. Isoxazolines as a chemical class have been shown to have no to very low affinity to the human GABA receptor and the GABA pathway is not activated in humans.

Vehicle of TP-03

The vehicle of TP-03 will be used to maintain masking of the BID dosing. Specifically, the concentrations of the excipients match TP-03, lotilaner ophthalmic solution, 0.25%.

4. STUDY OBJECTIVE

This study is intended to compare the safety and efficacy of two dosing regimens of TP-03, 0.25%, for the treatment of MGD in participants with *Demodex* lid infestation. Efficacy objectives will be evaluated by the assessment of the lower lid meibomian gland secretion score; assessment of erythema of the lid margins; [REDACTED] tear breakup time; [REDACTED] Safety will be determined by assessing adverse effects related to treatment [REDACTED].

5. STUDY DESIGN

This is a prospective, randomized, two-arm, double-masked, parallel pilot study of participants who have MGD and have *Demodex* lid infestation. Up to 40 participants will be enrolled. The treatment period will last for approximately 85 days and the follow-up period will last up to 175 days. The diagnosis of ocular demodicosis will be based on the presence of significant collarettes on the eyelashes and by the presence of mites. The diagnosis of MGD will be based on the specified meibomian gland secretion score and the tear breakup time criteria.

6. STUDY POPULATION

On Day 1, participants must be qualified to participate and baseline assessments are performed prior to the first administration of the study drug.

[REDACTED]

Inclusion criteria:

1. Male or female, aged ≥ 18 years of age
2. Participants must have all of the following **in at least one eye**:
 - More than 10 lashes with collarettes / cylindrical dandruff present on the upper lid
 - Presence of one or more mites with lash epilation of the upper and lower lids
 - For the 15 glands evaluated on the lower lid, have evidence of meibomian gland dysfunction based on a total meibomian gland secretion score between 12 to 32
 - Have at least Grade 1 erythema of the lower lid
 - Fluorescein tear breakup time < 10 seconds
 - Per meibography, the participant must have intact partial to full meibomian glands in at least 33% of the total meibomian gland area of the lower lid in the opinion of the investigator

[REDACTED]

[REDACTED]

[REDACTED]

4. Have a corrected distance visual acuity better than or equal to logMAR $+0.7$ as assessed by the Early Treatment of Diabetic Retinopathy Study (ETDRS) scale in each eye at Day 1
5. Willing to sign the informed consent, deemed capable of complying with the requirements of the study protocol and stated willingness and availability to comply with all study procedures for the duration of the study
6. For females of childbearing potential: use of acceptable methods of contraception* for at least 1 month prior to Day 1 and agreement to use such a method during study participation and for an additional four weeks after the end of study drug administration

Exclusion criteria:

1. Have used any artificial tear product within 24 hours of Day 1 or anticipated use during the study (with the exception of rescue therapy described in Section 15 of the protocol)
2. Use of systemic antihistamines within 30 days of Day 1

7. Treatment of blepharitis within 14 days of Day 1 (e.g., topical tea tree oil or hypochlorous acid) or unwilling to forego the use of these treatments for the duration of the study
8. The use of lid hygiene products such as lid scrubs, warm compresses or lid massage within 7 days of Day 1 or unwilling to forego the use of these treatments for the duration of the study

[REDACTED]

10. Have used artificial eyelashes, eyelash extensions or had other cosmetic eyelash or eyelid procedures (e.g., eyeliner tattooing, eyelash tinting, eyelash curling perm, etc.) within 7 days of Day 1 or be unwilling to forego their use during the study
11. Contact lens wear within 7 days of Day 1 or unwilling to forego contact lens wear for the duration of the study

21. Be pregnant or lactating at Day 1

[REDACTED]

[REDACTED]

[REDACTED]

[REDACTED]

7. STUDY OUTCOME MEASUREMENTS

7.1. EFFICACY PARAMETERS

Efficacy measures include the assessment of lower lid meibomian gland secretion; assessment of erythema of the lid margins; [REDACTED]; tear breakup time; [REDACTED]

[REDACTED]

7.2. SAFETY PARAMETERS

Safety measures include adverse events related to treatment [REDACTED]

[REDACTED]

8. CLINICAL EVALUATIONS

8.1. DAY 1

At the Day 1 visit, potential participants will be evaluated for eligibility and, if qualified, enrolled in the study. Prior to performing any study-specific procedures, potential participants must provide informed consent using the current IRB-approved informed consent form.

If potential participants fail to meet eligibility criteria, they can be screened one additional time on a different day. Rescreened participants should be assigned the same participant number that was used for the initial screening.

Procedures to be performed at the Day 1 visit include:

- Obtaining informed consent
- Obtaining the medical and ophthalmic history; concomitant medications
- CDVA

[REDACTED]

[REDACTED]

- TBUT
- Slit lamp biomicroscopy, including assessment of lid margin erythema
- Meibomian gland secretion assessment of lower lids

There will be two dosing arms, a BID active dosing and a TID active dosing arm.

Participants will be instructed to administer a single drop per eye from the first bottle in the morning and evening; a single drop per eye from the second bottle should be administered in the afternoon. The treatment period will be for approximately 85 days.

At Day 1, site staff will supervise the participant's first dose of the study medication. Participants should wash their hands prior to administration of the dose. Following drop administration, the participant will be asked to close their eyes for approximately 15 to 30 seconds and apply gentle pressure to the upper lid to express the medication across the upper and lower lid margins. The participant should be instructed to let the medication air dry on the lid without dabbing with a tissue.

On the day of in-office study visits, participants will be instructed not to use the study medication prior to the visit; the study medication can be administered after the visit has been completed.

If a dose is missed, participants will be instructed to administer the drop if it is at least an hour prior to the next dose. If it is less than an hour, the participant should simply dose the next drop.

8.2. DAYS 15 (± 4 DAYS) AND 29 (± 5 DAYS)

Procedures to be performed include:

- Concomitant medications review
- CDVA

- Slit lamp biomicroscopy, including assessment of lid margin erythema
- Meibomian gland secretion assessment of lower lids
- Assessment of adverse events

8.3. DAY 43 (-7/+6 DAYS) AND DAY 57 (-7/+10 DAYS)

Procedures to be performed include:

- Concomitant medications review
- CDVA
- Slit lamp biomicroscopy, including assessment of lid margin erythema
- Meibomian gland secretion assessment of lower lids
- Assessment of adverse events

8.4. DAY 85 (-13/+7 DAYS)

Procedures to be performed include:

- Concomitant medications review
- CDVA
- Slit lamp biomicroscopy including assessment of lid margin erythema

- Meibomian gland secretion assessment of lower lids
- Assessment of adverse events
- Collect study drug

At the Day 85 visit, the remaining study drug will be collected.

8.5. DAY 115 (+60 DAYS)

Participants who were exited from the study after completing dosing of study drug through Day 85 and participants who have not exited the study will be invited for an additional post-treatment follow-up visit on Day 115.

Procedures to be performed include:

- Reconsent the participants who were exited per protocol version 3.0 and participants who have not exited the study
- Concomitant medications review
- CDVA
- Slit lamp biomicroscopy including assessment of lid margin erythema
- Meibomian gland secretion assessment of lower lids
- Assessment of adverse events
- Study exit

At this visit, participants will be exited from the study provided they do not have any ongoing adverse events.

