10.1.1. RECONSENTING

Prior to performing any study-specific procedures specific to Day 115, potential study participants who exited the study per protocol version 3.0 and participants who have not exited the study will be provided with an IRB-approved informed consent form and given a chance to review and ask questions before written informed consent is obtained.

The potential study participant or enrolled study participant will be asked to sign and date the informed consent form. The individual explaining the consent will also sign and date the consent form as required. The original will be retained with the study participant's medical records and a copy will be provided to the study participant.

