10.2. PARTICIPANT ID ASSIGNMENT

While undergoing screening, potential study participants who sign an informed consent form will be identified by their initials and unique subject ID. For the initials, a dash (-) will be used in place of the middle initial for potential participants who have no middle name. The unique subject ID will consist of the site number followed by a hyphen and then the screening number. For each site, the screening number is a 4-digit number assigned in sequential order beginning with 0101.

If a potential study participant has provided written informed consent and met all eligibility criteria, the participant will be considered enrolled in the study. Once the participant has been enrolled, the site will supervise the administration of the first dose of the study medication.

Potential participants who have provided written informed consent but fail to meet eligibility criteria and are screened again on a different day will be assigned a new unique subject ID that is

different from their initial unique subject ID (next sequential screening number available at the site).

Participants who enrolled and exited the study but agree to return for the Day 115 visit will retain their originally assigned unique subject ID. Rescreened participants who enrolled and exited the study will retain their second unique subject ID assigned.

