Temporary discontinuation of the study treatment could include the onset of such conditions as allergic conjunctivitis or signs or symptoms of eyelid allergy (e.g., injection, swelling, itching, etc.). Per investigator discretion, the study treatment could be discontinued until such a time that the adverse event has shown sufficient improvement such that the study treatment could be restarted. Re-challenging with the study treatment could help to determine if the adverse event is related to the study drug. It should be noted that discontinuation from use of the study treatment does not mean discontinuation from the study, and remaining study procedures should be completed as indicated by the study protocol.

The following actions must be taken if a participant fails to return to the clinic for a required study visit:

- The site will attempt to contact the participant and reschedule the missed visit as soon as possible, counseling the participant on the importance of continuing the administration of the study drug and of maintaining the assigned visit schedule. In addition, the site should ascertain if the participant wishes to and/or should continue in the study.
- Before a participant is deemed lost to follow-up, the investigator or designee will make every effort to regain contact with the participant (where possible, three telephone calls and, if necessary, a certified letter to the participant's last known mailing address or local equivalent methods). These contact attempts should be documented in the participant's medical record or study file.

- Should the participant continue to be unreachable, he or she will be considered to have discontinued the study with a primary reason of lost to follow-up.

The principal investigator reserves the right to discontinue the study for any safety, ethical or administrative reason at any time.

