12.4. MISSING DATA

Missing data will not be imputed.

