12.9. FINAL REPORT

Once all participants have completed the Day 85 assessment or have been exited from the study and all corresponding data has been received and corrected, the study database for visits through Day 85 will be locked. Once the data has been locked, the treatment assignments will be unmasked and a complete analysis of the results will be performed and a final report will be prepared. Once all participants have been exited from the study and all additional data has been received and corrected, the complete database including the additional data collected through Day 115 will be locked. An addendum to the final report will be prepared to include the additional follow-up results through the Day 115 assessment.

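### Section 8.5 requires completed dosing for Day 115 only of participants who have already exited, so two identical early stoppers are treated differently and the Day 115 set is partly selected on a post-randomisation event

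*Protocol*

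**What the plan says.** Section 8.5 of the protocol is the only place that says who is invited to the added Day 115 visit: "Participants who were exited from the study after completing dosing of study drug through Day 85 and participants who have not exited the study". The first half of that sentence carries a dosing condition and the second half does not.

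The procedures list in the same section describes the exited group differently: "Reconsent the participants who were exited per protocol version 3.0 and participants who have not exited the study". Section 10.1.1 uses the same description: "potential study participants who exited the study per protocol version 3.0 and participants who have not exited the study". Section 10.2, on numbering, says: "Participants who enrolled and exited the study but agree to return for the Day 115 visit will retain their originally assigned unique subject ID". None of these three repeats the dosing condition. The available text does not define what it means to have exited under version 3.0.

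Section 11 separates stopping the drug from leaving the study: "discontinuation from use of the study treatment does not mean discontinuation from the study, and remaining study procedures should be completed". This sits in a paragraph on temporary interruption, but its wording is general.

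On the use of the data, Section 12.4 states "Missing data will not be imputed", and Section 12.9 states "An addendum to the final report will be prepared to include the additional follow-up results through the Day 115 assessment". That addendum follows the Day 85 lock, unmasking and final report.

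**The concern.** Whether a participant finishes dosing is known only after randomisation and may depend on treatment. Section 11 lists lack of efficacy and adverse events among the reasons for discontinuation, and eyelid allergy signs as grounds for pausing treatment. The clinical hypothesis itself contrasts TID and BID on improvement and on ocular irritation. A rule that admits some participants to a visit only if they finished dosing can therefore select on the outcome, and unequally by arm.

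Day 115 is the only visit scheduled after the treatment period for all participants. With no imputation, anyone not invited is simply absent from the addendum. Disposition is touched too: Section 11 counts a participant as having completed the study only when Day 115 has been assessed, and Section 17 reports completers, so an exited early stopper who is not invited cannot count as one.

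**Working it through.** The protocol gives no figure on this point to reproduce. The check is a comparison of passages, followed by an illustration of scale.

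**1. The passages side by side**

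| Place | What it governs | Exited participants | Not yet exited |
|---|---|---|---|
| 8.5, opening sentence | Invitation | Only if dosing was finished through Day 85 | All |
| 8.5, reconsent bullet | Consent at the visit | Exited under version 3.0, no dosing condition | All |
| 10.1.1 | Consent | Exited under version 3.0, no dosing condition | All |
| 10.2 | ID numbers | Enrolled, exited and willing to return, no dosing condition | Not addressed |

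**2. Two participants.** A and B both stop the drug at Day 40 and attend every visit through Day 85, as Section 11 asks. A exits at Day 85 under version 3.0. B has not exited when the amended protocol takes effect. Under the opening sentence of 8.5, A is not invited and B is. They differ only in exit date.

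**3. Possible intents.** If Day 115 is meant to show durability after a full course, the second half of the sentence admits people it should not. If it is meant for everyone, the first half excludes people it should not. Neither intent fits the whole sentence.

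**4. Scale, on assumed inputs.** The plan is for up to 40 participants at 1:1, so at most 40 / 2 = 20 per arm. The number left out and their outcomes are not in the documents and are assumed here.

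If a proportion p of an arm is left out, and their mean change is worse than that of the others by a gap, then

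observed mean − full-arm mean = p × gap.

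With the same gap in both arms, the shift in the between-arm difference is (difference in number left out / 20) × gap. In SD units, for a gap of 0.25 to 1.0 SD:

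- no difference: 0
- 1 more in one arm: 0.05 × 0.25 to 0.05 × 1.0 = 0.0125 to 0.05 SD
- 2 more: 0.10 × 0.25 to 0.10 × 1.0 = 0.025 to 0.10 SD
- 4 more: 0.20 × 0.25 to 0.20 × 1.0 = 0.05 to 0.20 SD

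On the gland secretion score (range 0 to 45), suppose 4 of 20 TID and 1 of 20 BID participants are left out. The shift is (0.20 − 0.05) × gap = 0.15 × gap: 0.3 points at a gap of 2, 0.75 at 5 and 1.2 at 8, in favour of TID. Exchange the arms and the sign reverses. With 1 of 20 left out in each arm and a gap of 5, each arm is overstated by 0.05 × 5 = 0.25 points and the between-arm shift is 0.

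These figures assume that everyone left out had already exited and would have attended if invited. Some early exits are withdrawals or losses to follow-up who may not return under any wording, so the part due to the sentence in 8.5 may be smaller.

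**The case against.** The best defence has five parts.

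- **There is no rival invitation rule.** Section 10.1.1 governs consent and 10.2 governs numbering. They are silent on the dosing condition rather than opposed to it, and an exit under version 3.0 can be read as the scheduled exit after Day 85. This stands. A reader might infer that sites will apply different invitation rules; the undefined phrase makes that possible, but the documents do not show it.
- **Day 115 is not restricted to dosing completers.** This also stands. A reader might infer a completers-only comparison from the first half of the sentence, but the second half invites everyone still in the study, and Section 11 keeps treatment stoppers there.
- **Restricting exited participants to those who finished the course is defensible.** At Day 115 a Day 40 stopper is 115 − 40 = 75 days off drug and a completer 115 − 85 = 30. This would justify a restriction applied to both groups. It does not justify one applied only to those already exited.
- **Safety follow-up is covered.** Section 11 follows participants discontinued for adverse events until resolution, if possible, or stability. A reader might infer that late safety information is lost; what is lost is the scheduled Day 115 examination.
- **The stakes are low.** This is a pilot, and Day 115 goes into an addendum. Dependence on exit date alone should fall roughly equally on both arms under blocked, masked randomisation. No visible text names a Day 115 BID-TID test, although Section 12.7 does not limit its comparison of regimens to particular visits. The SAP's sections on populations, disposition and missing data are listed in its contents but their text is not available, so attendance reporting cannot be called absent.

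**Conclusion.** The point holds in a limited form. For participants already exited, 8.5 conditions the invitation on a post-randomisation event; for those not yet exited it does not. The Day 115 set is therefore mixed: dosing completers among the exited, plus everyone still in the study. With observed data only, the exited early stoppers are missing from it.

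The size and direction of any BID-TID bias are unknown. The ranges of 0.0125 to 0.20 SD and 0.3 to 1.2 points come wholly from assumed counts and gaps, and should not be read as an estimate or as evidence that the plan favours TID. If stopping is equal and for the same reasons, the between-arm bias is about zero, though the level after treatment may still be overstated in both arms. The Day 85 analysis is untouched. The correction is worth making because it is small and removes an avoidable selection from data that will be reported.

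**What to change.** In Section 8.5, remove the dosing condition from the opening sentence and use the population of Section 10.1.1: participants who exited under protocol version 3.0, stated to include those who stopped treatment early, and participants who have not exited. Exclude those who withdrew consent to contact.

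In the addendum, give by arm the numbers randomised, invited and attending Day 115, with dosing status. Include attending early stoppers in the main Day 115 table, with a flag. The disposition row is useful even if nobody was left out, because a reader can then see that.

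The cost is one sentence, one disposition row and perhaps a few visits of a type already planned. The downside is that some Day 115 participants will have had shorter exposure and a longer time off drug, which the flag makes visible.
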